1.2.1.2.5. Overall Survival

Overall Survival (OS) is defined as the time from the date of the first dose of study treatment to the date of death by any cause. Patients who are still alive at the time of the analysis data cutoff date, or who have become lost to follow-up will be censored at their last date known to be alive on or before the date of data cutoff.

OS in months is calculated as (date of death/last known to be alive – date of the first dose +1)/30.4375. Patients lacking any dates which support patients still alive beyond the first dose date will have their OS censored at the date of the first dose.

1.2.1.3. Exploratory Endpoints:

1.2.1.3.1. Pharmacodynamic (PD) and Biomarker Endpoints

Biomarkers using peripheral blood samples and tumor tissue samples in patients receiving DSP-7888 Dosing Emulsion in combination with pembrolizumab or nivolumab may be evaluated for correlation with the following immunologic changes and/or clinical responses. The endpoints includes:

1.2.1.3.1.1. WT1-specific CTL induction activity in blood samples

WT1 specific CTL induction activity will be measured every 2 cycles pre-dosing until dosing is discontinued (eg, Cycle 7, 9, 11, 13) for phase 1b, and at screening and, during treatment, prior to each dose Cycle 5, 7, 9 and subsequent assessments every 4 Cycle (Cycle 13, 17, 21 etc.) for phase 2 part.

Depending on the HLA types, WT1 -specific CTL Induction will be measured differently.

For patients with HLA-A*02:01 **NOT** HLA-A*02:06, below measurements will be measured and analyzed:

- %WT137-45 Tet+ in CD8+ (P7/P6),
- CD8+WT137-45 Tet+ (P7) Event #,

For patients with HLA-A*02:01/HLA-A*02:06, below measurements will be measured and analyzed:

- %WT137-45 Tet+ in CD8+ (P7/P6),
- %WT1126-134 Tet+ in CD8+ (P8/P6),
- CD8+WT137-45 Tet+ (P7) Event #,
- CD8+WT1126-135 Tet+ (P8) Event #

For patients with HLA-A*24:02, below measurements will be measured and analyzed:

- %WT1235-243 Tet+ in CD8+ (P9/P6),
- CD8+WT1235-243 Tet+ (P9) Event #

For patients with HLA-A*03:01 or HLA-B*15:01, below measurements will be measured and analyzed:

- %WT1126-134 Tet+ in CD8+,
- CD8+WT1126-134 Tet+ Event#

HLA-A*03:01 or HLA-B*15:01 will only be available for phase 2 not in phase 1b.

1.2.1.3.1.2. Other PD and Biomarker Endpoints

- WT1 expression level via chromogenic in situ hybridization (CISH) and PD-L1 expression level via immunohistochemistry (IHC)

WT1 expression level via chromogenic in situ hybridization (CISH) includes % Tumor cells WT1 positive; and WT1 Tumor H-score

- CD8+ cell density in tumor tissues
- Tumor infiltrating lymphocytes (TILs) profiling in tumor tissues
- Immune profiling in tumor tissues with tumor inflammation signature analysis
- Mutation status and tumor mutation burden (TMB) in tumor tissues

1.2.1.3.2. Progression Free Survival Ratio

PFS (-1) is defined as the date of initiation of the previous (penultimate) treatment regimen to the date of assessment of progression by RECIST (v.1.1).

PFS ratio is defined as PFS/PFS (-1) ratio using RECIST (v.1.1).

1.2.2. Phase 2

A summary of objectives, endpoints, and assessments of Phase II of the study is presented in [Table 7](#) below.

Table 4: Summary of Objectives and Endpoints for Phase 2

	Objectives	Endpoints
Phase 2		
Primary	To evaluate the preliminary antitumor activity of DSP-7888 Dosing Emulsion administered with pembrolizumab in terms of ORR in patients with platinum-resistant ovarian cancer (PROC)	ORR, defined as the proportion of patients who have achieved confirmed CR or PR, evaluated using RECIST (v.1.1) based on investigator assessment
Secondary	To evaluate the preliminary clinical activity of DSP-7888 Dosing Emulsion in combination with pembrolizumab in terms of DOR, DCR, PFS, 6 months PFS Rate, and OS of DSP-7888 Dosing Emulsion administered in combination with pembrolizumab in PROC	
 1. DOR, defined as the time from the first documentation of a response (CR or PR) until time of first documentation of disease progression by RECIST (v.1.1), or death by any cause 2. DCR, defined as the percentage of patients who have achieved BOR of CR, PR, or SD per RECIST (v.1.1) 3. PFS, defined as the time from the date of the first dose of study treatment to the earlier date of assessment of progression

	Objectives	Endpoints
		
by RECIST (v.1.1), or death by any cause
 
4. 6 months PFS Rate, defined as the proportion of patients who neither progressed by RECIST (v.1.1) nor died before 6 months (24 weeks) from the first study treatment
 
5. OS, defined as the time from the date of the first dose of study treatment to the date of death by any cause

	To determine ORR, DCR, PFS, and iDOR per iRECIST of DSP-7888 Dosing Emulsion administered in combination with pembrolizumab in PROC	
1. immune ORR (iORR), defined as proportion of patients who have achieved confirmed immune complete response (iCR) or immune partial response (iPR), evaluated using iRECIST based on investigator assessment
 
2. immune DCR (iDCR), defined as the percentage of patients who have achieved BOR of iCR, iPR, or iSD per iRECIST
 
3. immune PFS (iPFS), defined as the time from the date of the first dose of study treatment to the earlier date of assessment of progression* by iRECIST, or death by any cause
 
4. immune DOR (iDOR), defined as the time from the first documentation of response (iCR or iPR) until time of first documentation of disease progression by iRECIST, or death by any cause
 
* The event date to be used for calculation of PFS should be the first date at which progression criteria are met (ie, the date of immune unconfirmed progressive disease [iUPD]) provided that immune confirmed progressive disease [iCPD] is confirmed at the next assessment. If iUPD occurs, but is disregarded because of later iSD, iPR, or iCR, that iUPD date should not be used as the progression event date

	To evaluate the safety and tolerability of DSP-7888 Dosing Emulsion administered with pembrolizumab	Frequency and intensity of AEs using Common Terminology Criteria for Adverse Events (CTCAE) v 4.03
Exploratory	To determine the PFS rate as an evaluation of treatment benefit of	PFS rate is defined as PFS1/PFS (-1) ratio using RECIST (v.1.1)

	Objectives	Endpoints
	DSP-7888 Dosing Emulsion administered with pembrolizumab	
 1. PFS1 is defined as the time from the date of the first dose of study treatment to the earlier date of assessment of progression by RECIST (v.1.1), or death by any cause 2. PFS (-1) is defined as the date of initiation of the previous (penultimate) treatment regimen to the date of assessment of progression by RECIST (v.1.1)
	To evaluate the antitumor activity of DSP-7888 Dosing Emulsion administered with pembrolizumab in terms of the CA-125 response rate and time to progression with CA-125 criteria in PROC	
 1. CA-125 response rate is defined as proportion of patients who have achieved response using the Gynecologic Cancer InterGroup (GCIg) CA-125 response definition 2. Time to progression with CA-125 is defined as the time from the date of the first dose of study treatment to the earlier date of assessment of progression by GCIg CA-125 progression definition or death by any cause
	To characterize PD or potential predictive biomarkers and their relationship to clinical activity	
Biomarkers using peripheral blood samples and tumor tissue samples in patients receiving DSP-7888 Dosing Emulsion in combination with pembrolizumab may be evaluated for correlation with the following immunologic changes and/or clinical responses
 
 1. WT1-specific CTL induction activity in blood samples 2. WT1 expression level via CISH and PD-L1 expression status (CPS) via IHC in tumor tissue 3. CD8+ cell density in tumor tissues 4. TILs profiling in tumor tissues 5. Immune profiling in tumor tissues with tumor inflammation signature analysis 6. Mutation status and mutational burden analysis in tumor tissues 7. HLA typing

*Note: These samples must contain sufficient tumor tissue. Details of the biopsy time points are described in the SOA in Protocol Amendment 6 Table 9.

1.2.2.1. Primary Endpoint:

Primary Endpoint of phase 2 part is ORR per RECIST (v.1.1) based on investigator assessment (refer to Section 1.2.1.2.1 for the definition.)

1.2.2.2. Secondary Endpoints:

Secondary endpoints include DOR, DCR, PFS, 6 – month PFS rate per RECIST (v1.1) (refer to for Section 1.2.1.2.1 Section 1.2.1.2.3 for definitions.) ; iORR, iDCR , iDOR and iPFS per iRECIST based on investigator assessment (refer to Section 1.2.1.2.2 Section 1.2.1.2.4 for definition) ; and OS (refer to Section 1.2.1.2.5 for definition).

Safety assessment of frequency and intensity of AEs assessed according to CTCAE v4.03. also included a secondary endpoint.

1.2.2.3. Exploratory Endpoints:

1.2.2.3.1. Progression Free Survival Ratio

PFS (-1) is defined as the date of initiation of the previous (penultimate) treatment regimen to the date of assessment of progression by RECIST (v1.1). PFS ratio is defined as PFS/PFS (-1) ratio using RECIST (v.1.1).

1.2.2.3.2. CA-125 and Time to progression with CA-125

For Phase 2, the CA-125 Response and time to CA-125 progression will be analyzed as exploratory endpoints using FAS as exploratory endpoints.

CA-125 response rate is defined as proportion of patients who have achieved response using the Gynecologic Cancer InterGroup (GCIg) CA-125 response definition. (see Appendix 1) . A CA-125 response is defined as at least a 50% reduction in CA-125 levels from latest baseline sample from C1D1. In addition, those patients who have a CA-125 response and whose CA-125 level falls to within the normal range can be classified as CA-125 complete responders. Patients can be evaluated according to CA-125 only if they have a baseline sample that is at least twice the upper limit of normal (ULN) range within 28 days of C1D1. Patients who have an initial CA-125 that was less than twice the ULN range will be evaluated for CA-125 progression only.

Time to progression with CA-125 is defined as the time from the date of first dose of study treatment to the earlier date of assessment of progression by GCIg CA-125 progression definition or death by any cause. (See Appendix 1) CA-125 progression is defined as the progressive serial elevation of serum CA-125, according to the following modified Gynecologic Cancer Inter-Group (GCIg) criteria ([Appendix 1](#))

- Patients with elevated CA-125 pretreatment must show evidence of CA-125 greater than or equal to 2 times the nadir value in the 28-day period before C1D1 on 2 occasions at least 1 week apart,
- Patients with CA-125 in the normal range pretreatment must show evidence of CA-125 greater than, or equal to, the ULN.

Table 9: Summary of CA-125 Assessment

Response:	Definition:	Applies to:
CA-125 complete response	At least a 50% reduction in CA-125 levels from baseline and whose CA-125 level falls to within the normal range	Those patients who have a baseline sample that is at least twice the ULN range in CA-125 partial 28 days of C1D1
CA-125 partial response	At least a 50% reduction in CA-125 levels from baseline, but not within normal range	

Non-PR/non-PD	Neither at least a 50% reduction in CA-125 levels from baseline nor progression	
Not PD	Not meeting the criteria of progression (not evaluable population for CA-125 response)	Patients who have an initial CA-125 that was less than twice the ULN range
Progression	2-fold increase from the baseline CA-125 (if above the ULN at baseline) or 2-fold greater than the ULN (if below the ULN at baseline)	All patients

ULN = upper limit of normal

Time to progression is determined by the first date of the assessment that showed 2 times the ULN or nadir on 2 occasions at least 1 week apart, and will be calculated as:

Time to CA-125 Progression (months) = (Date of Progression / censor – Date of first dose + 1) / 30.4375.

Patients last known to be progression-free are censored at the date of the last overall assessment that verified lack of CA-125 progression (either scheduled or unscheduled visit).

1.2.2.3.3. Pharmacodynamic (PD) and Biomarker Endpoints

Biomarkers using peripheral blood samples and tumor tissue samples in patients receiving DSP-7888 Dosing Emulsion in combination with pembrolizumab may be evaluated for correlation with the following immunologic changes and/or clinical responses

- WT1-specific CTL induction activity in blood samples (refer to Section 1.2.1.3.1.1)
- WT1 expression level via CISH and PD-L1 expression status (CPS) via IHC in tumor tissue
- CD8+ cell density in tumor tissues
- TILs profiling in tumor tissues
- Immune profiling in tumor tissues with tumor inflammation signature analysis
- Mutation status and mutational burden analysis in tumor tissues
- HLA typing: potential include: HLA-A*02:01, HLA-A*02:06, HLA-A*24:02, HLA-A*03:01 and HLA-B*15:01.

2. HYPOTHESES AND DECISION RULES

2.1. Statistical Hypotheses

There is no formal hypothesis for this study including phase 1b and phase 2 part.

2.2. Statistical Decision Rules

For Phase 2 Cohort Only

There is no formal hypothesis testing for the Phase 2 cohort. A Bayesian decision-making framework will be employed to quantify whether proof of concept (POC) can be established based on the overall response rate (ORR) by Week 24 from the final analysis for the overall population and/or the CPS < 10 subpopulation. The POC is established at the final analysis if either or both of the following 2 conditions are met:

- In the overall population, 70% credible interval of ORR with 10% in the left tail and 20% in the right tail will be calculated: if lower bound $\geq 8\%$ and upper bound $\geq 21\%$ (where 8% is the reference value [Protocol Amend 6, Section 4.3.1; Matulonis, 2019] and 21% is the target value of ORR in the overall population), the study will achieve POC.
- In the CPS < 10 subpopulation, 50% credible interval of ORR with 20% in the left tail and 30% in the right tail will be calculated: if lower bound $\geq 5\%$ and upper bound $\geq 15\%$ (where 5% is the reference value [Protocol Amend 6, Section 4.3.1; Matulonis, 2019] and 15% is the target value of ORR in CPS < 10 subpopulation), the study will achieve POC.

The interim monitoring analysis for futility early efficacy assessment will be conducted using a Bayesian method and will start after the first 20 patients have response evaluation, withdraw, or die by Week 24.

- If the posterior probability of ORR $\geq 21\%$ in the overall population is $\leq 2.5\%$ AND the posterior probability of ORR $\geq 15\%$ in the CPS < 10 subpopulation is $\leq 2.5\%$, the study is futile and further enrollment will be stopped.
- If the posterior probability of ORR $\geq 21\%$ in overall population is $\geq 80\%$ AND the posterior probability of ORR $\geq 15\%$ in CPS < 10 subpopulation is $\geq 70\%$, then early success is met and further enrollment may be stopped.
- Otherwise, the enrollment will continue as is until 40 patients.

The above decision rules for interim analysis are non-binding.

2.3. Sample Size Considerations and Power Calculation

In Phase 1b of the study, there will be approximately 6 to 12 patients for each arm, up to a total of 24 patients. As part of these 24 patients, an enrichment cohort of 10 patients will be enrolled into Phase 1b. If anti-tumor activities are observed in any tumor type, additional patients may be enrolled for further assessment.

In Phase 2 of the study, approximately 20 to 40 patients will be enrolled. Additional patients may be enrolled to further assess anti-tumor activities in the subgroups of interest. However, the total sample size of Phase 2 cannot exceed 60 patients. In total, approximately 64-84 patients will be enrolled in the study.

3. ANALYSIS POPULATIONS

3.1. Full Analysis Set

The Full Analysis Set (FAS) consists of all patients who receive at least 1 full or partial dose of study treatment (DSP-7888 Dosing Emulsion, nivolumab, or pembrolizumab). Patients will be classified according to the treatment assigned (dose level and schedule).

3.2. Safety Set

The Safety Set (SS) consists of all patients who receive at least 1 full or partial dose of study treatment (DSP-7888 Dosing Emulsion, nivolumab, or pembrolizumab). Patients will be classified according to the treatment received (dose level and schedule), where treatment received is defined as the actual treatment if the patients took at least 1 dose of that treatment or the first treatment received if the assigned treatment was never received.

Safety analysis set will be used for all safety related analyses such as AE, concomitant medication, laboratory tests, and vital signs and drug exposure evaluation.

3.3. Treatment Allocation

Phase 1b (a dose search part and an enrichment part) of this study, there will be 2 arms: Arm 1 and Arm 2:

- Arm 1: DSP-7888 Dosing Emulsion + nivolumab combination:
- Arm 2: DSP-7888 + pembrolizumab combination:

Phase 1b patients who get at least one dose of DSP-7888 and nivolumab will belong to Arm 1; and who at least one dose of DSP-7888 and pembrolizumab will belong to Arm 2.

Phase 2 part of the study, patients will be treated with DSP-7888 Dosing Emulsion in combination with pembrolizumab.

4. DATA HANDLING CONVENTIONS

4.1. Data Presentation Conventions

Means and medians will be presented to 1 more decimal place than the recorded data. The standard deviations (SDs) will be presented to 2 more decimal places than the recorded data. Confidence intervals about a parameter estimate will be presented using the same number of decimal places as the parameter estimate.

4.2. Baseline Definition

Baseline is defined as the most recent, non-missing value prior to or on the first study drug dose date within 28 days from first dose.

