**Table 7: Schedule of Assessments (Arm 1, Combination of DSP-7888 Dosing Emulsion and Nivolumab [14-Day Study Cycles])**

Tests and Procedures	Pre-Screening	Pre-Study Evaluation	On-Study Evaluations a									End of Treatment	Follow-Up For OS
			Cycle 1		Cycle 2		Cycle 3	Cycle 4	Cycle 5	Cycle 6	Cycle 7+		
Week			0	1	2	3	4	6	8	10	12+	30 days after last DSP-7888 Dosing Emulsion dose	Every 3 months after date off treatment
Day	Any time before enrollment	Within 28 days prior to first dose of study drug	1	8	15	22	29	43	57	71	85+		
Window		28 days	±2 days	±2 days	±2 days	±2 days	±2 days	±2 days	±2 days	±2 days	±2 days		
Pre-screening consent	X												
HLA-typing (A/B locus and DRB1 locus)	X												
Informed consent		X											
Inclusion/exclusion review		X											
Medical and cancer history		X											
Physical examination		X	X		X c		X c	X					
Serum pregnancy test, if applicable		X											
ECOG performance status		X			X		X	X	X	X	X	X	
Complete vital signs		X	X		X		X	X	X	X	X	X	
Body weight		X	X		X		X	X	X	X	X	X	
Hematology		X		X	X	X	X	X	X	X	X	X	
Clinical chemistry		X		X	X	X	X	X	X	X	X	X	
Thyroid function test		X			X		X	X	X	X	X	X	
Urinalysis		X		X	X	X	X	X	X	X	X	X	
Pulse oximetry		X	X		X		X	X	X	X	X	X	
Blood samples for Hepatitis B/C & HIV		X											
ECHO/MUGA		X			X			X			X d	X	
12-lead electrocardiogram		X	X e		X e			X			X f	X	
Tumor tissue samples for biomarkers g		X h									X i		
Tumor tissue samples for future biomarker analysis j		X									X i		

Tests and Procedures	Pre-Screening	Pre-Study Evaluation	On-Study Evaluations a									End of Treatment	Follow-Up For OS
			Cycle 1		Cycle 2		Cycle 3	Cycle 4	Cycle 5	Cycle 6	Cycle 7+		
Week			0	1	2	3	4	6	8	10	12+	30 days after last DSP-7888 Dosing Emulsion dose	Every 3 months after date off treatment
Day	Any time before enrollment	Within 28 days prior to first dose of study drug	1	8	15	22	29	43	57	71	85+		
Window		28 days	±2 days	±2 days	±2 days	±2 days	±2 days	±2 days	±2 days	±2 days	±2 days	+7 days b	
Blood samples for CTL induction k		X l			X m		X m		X m		X m,n	X	
Blood samples for future biomarker analysis o		X l			X m		X m		X m		X m,n	X	
Concomitant medications		X	X	X	X	X	X	X	X	X	X	X	

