Adverse events p		X	X	X	X	X	X	X	X	X	X	X	
Administer DSP-7888 Dosing Emulsion			X	X	X	X	X	X	X	X	X		
Administer nivolumab							X	X	X	X	X		
Follow-up for overall survival													X q
Objective disease assessment f		X	First post-treatment assessment at Week 4 (Cycle 3), followed by one at Week 12 (Cycle 7), then 2 subsequent assessments every 6 weeks at Week 18, Week 24 (Cycle 10, Cycle 13), and finally every 12 weeks (Cycle 19 and every 6 cycles) until disease progression. s										

Abbreviations: AE = adverse event; CT = computed tomography; CTCAE = Common Terminology Criteria for Adverse Events; CTL = cytotoxic T lymphocyte; ECG = echocardiogram; ECOG = Eastern Cooperative Oncology Group; ECHO = echocardiogram; FFPE = formalin-fixed and paraffin embedded; HIV = human immunodeficiency virus; HLA = human leukocyte antigen; ICF = informed consent form; iRECIST = immune Response Evaluation Criteria in Solid Tumors MRI = magnetic resonance imaging; MUGA = multiple gated acquisition; OS = overall survival; PD-L1 = programmed death ligand 1; PET = positron emission tomography; PBMC = peripheral blood mononuclear cells; RECIST = Response Evaluation Criteria in Solid Tumors; TIL = tumor-infiltrating lymphocytes; TIS = tumor immune signature; WT1 = Wilms Tumor 1

a All tests must be performed PRIOR to injection of study treatment, with the exception of ECG.

b Complete End of Treatment assessment procedures before patient receives new anti-cancer treatment.

c Inspection of prior injection sites will be done at each administration of the vaccine.

d . From Cycle 4, ECHO/MUGA tests for ejection fraction will be done on Day 1 every 6th cycle (eg, Cycle 10, 16, 22).

e Obtained at least 2 hours post-dose of DSP-7888 Dosing Emulsion.

f From Cycle 4, 12-lead electrocardiograms will be performed on Day 1 of every 3rd Cycle (eg, Cycle 7, 10, 13).

g It should be ensured that a total of at least 23 slides of archival samples and/or the equivalent amount of archival tissue block and/or fresh biopsy samples from the enrolled patients are available. These samples must contain sufficient tumor tissue.

- h Collection of tumor tissue samples at Pre-Study evaluation is mandatory. Either archival tissue or fresh biopsy samples at Pre-study evaluation would be acceptable. Collection of fresh biopsy samples is required, if medically feasible.

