##### **11.1.1.3. Cardiac Assessments**

Cardiac assessments, including ECHO/MUGA scans for ejection fraction; 12-lead resting ECG in triplicate, including heart rate, PR interval, QRS duration, QTcF intervals, and ECG findings; and pulse oximetry assessments will be obtained during Screening and then according to [Table 7](#), [Table 8](#), and [Table 9](#).

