## 12. STATISTICS

### 12.1. Statistical Methods

Detailed methodology for the statistical analyses of the data collected in this study will be documented in the statistical analysis plan (SAP), which will be maintained by [REDACTED]. The SAP may modify the plans outlined in the protocol; however, any major modifications of the primary endpoint definition and/or its analysis will also be reflected in a protocol amendment.

In general, all efficacy and safety endpoints will be analyzed using descriptive statistics (n, mean, standard deviation, median, and ranges for continuous variables; frequencies and percentages for categorical variables).

All deviations related to conduct of the study, patient management, or patient assessment will be identified, evaluated, and closed before database lock and will be described in the final CSR. Protocol deviations are not allowed for inclusion or exclusion criteria.

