#### **12.1.4. Demographic and Baseline Characteristics**

Baseline is defined as the last non-missing measurement taken before receiving the first dose of study drug. All applicable demographic and baseline characteristics will be summarized with descriptive statistics.

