1. INTRODUCTION

This statistical analysis plan (SAP) describes the statistical methods that will be used during the analysis and reporting of data collected under Sumitomo Pharma Oncology Protocol DSP7888-102CI. This SAP should be read in conjunction with the study protocol and electronic case report forms (eCRFs). This version of the SAP has been developed using BBI-DSP7888-102CI_aCRF_21Jul2020 FINAL.pdf.

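### SAP 4.2 sets baseline by date, so the Phase 1b Day 1 ECG, scheduled after the first DSP-7888 injection, becomes the QT/QTcF baseline

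*SAP*

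**What the plan says.** SAP 4.2 gives one general rule: baseline is "the most recent, non-missing value prior to or on the first study drug dose date within 28 days from first dose". Protocol 12.1.4 gives a different one: "Baseline is defined as the last non-missing measurement taken before receiving the first dose of study drug".

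Protocol Table 7 (Arm 1) marks the "12-lead electrocardiogram" at screening, Cycle 1 Day 1, Cycle 2 (Day 15) and later visits. The Day 1 and Day 15 entries carry the footnote "Obtained at least 2 hours post-dose of DSP-7888 Dosing Emulsion". Another footnote reads "All tests must be performed PRIOR to injection of study treatment, with the exception of ECG". Table 8 (Arm 2) has the same pattern, with Day 1 and Day 22 as the footnoted visits. Table 9, the current Phase 2 schedule, has no Day 1 ECG.

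SAP 5.4.3 uses baseline in three summaries: the normal/abnormal shift to worst post-baseline result, the QT and QTcF categories at baseline and at post-baseline maximum, and the maximum change from baseline (up to 30, above 30 to 60, above 60 ms). It defines post baseline as records after the first dose up to 30 days after the last. It does not define an ECG baseline.

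**The concern.** The SAP and protocol rules agree for any test done before injection. The Phase 1b ECG is the one test exempted from that order, so it is where they part. In a patient who follows the schedule, the most recent value on the dosing date is a post-dose ECG, and SAP 4.2 prefers it to screening. This is the scheduled case, not a rare deviation.

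The final report has been cut back to safety (SAP 5), and the ECG summaries are among the outputs kept. A reference value taken after exposure can hide a change that is already present at that ECG, or create an apparent change where there is none. SAP 5.4.3, applied by clock time, also counts the same record as post baseline, which leaves the programmer with one ECG in two roles.

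**Working it through.** **Which record each rule selects (Phase 1b, current schedule)**

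| Record | Timing | Protocol 12.1.4 | SAP 4.2 | SAP 5.4.3 |
|---|---|---|---|---|
| Screening ECG | within 28 days before dose | baseline | superseded | – |
| Day 1 ECG | at least 2 h after DSP-7888 | not baseline | baseline | post baseline if applied by clock time |
| Later ECGs | Cycle 2 onward | not baseline | not baseline | post baseline |

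**Effect on change from baseline.** Let S be screening, D the Day 1 post-dose value and L the later maximum (ms).

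- Pre-dose baseline: max(D, L) − S
- SAP 4.2, Day 1 also counted as post baseline: max(D, L) − D
- SAP 4.2, Day 1 baseline only: L − D

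The first two differ by exactly D − S. The documents contain no clinical QTcF values, so these are illustrative:

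| S / D / L | Pre-dose baseline | SAP 4.2, counted twice | SAP 4.2, baseline only |
|---|---|---|---|
| 420 / 424 / 455 | +35 (>30–60) | +31 (>30–60) | +31 (>30–60) |
| 420 / 425 / 455 | +35 (>30–60) | +30 (≤30) | +30 (≤30) |
| 420 / 425 / 485 | +65 (>60) | +60 (>30–60) | +60 (>30–60) |
| 420 / 410 / 445 | +25 (≤30) | +35 (>30–60) | +35 (>30–60) |
| 440 / 485 / 450 | +45 (>30–60) | 0 (≤30) | −35 (≤30) |

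A category changes only when D − S carries the result across a cut-off (row 1 against row 2). In the last row the absolute categories are ≤450 to >480–500 with a pre-dose baseline. They become >480–500 to >480–500 if the record is counted twice, and >480–500 to ≤450 if it is baseline only. In that last reading the Day 1 peak leaves the post-baseline table.

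**How often.** Simulation, 400,000 draws: independent normal visit values, with screening, Day 1 and four later ECGs (Cycle 2, Cycle 3 or 4, Week 12, end of treatment, as in Tables 7 and 8). Protocol 11.1.1.3 calls for "12-lead resting ECG in triplicate", so two SDs were used: 10 ms per visit value, and 10/√3 = 5.77 ms for the mean of three independent tracings. Tracings within a visit are correlated, so the triplicate case lies between the two. The table gives P(maximum change > 30 ms), screening baseline v SAP 4.2 baseline:

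| Assumed shift | SD 10 | SD 5.77 |
|---|---|---|
| None | 6.5% v 5.4% | 0.06% v 0.04% |
| 5 ms, Day 1 onward | 13.3% v 5.5% | 0.49% v 0.05% |
| 10 ms, Day 1 onward | 24.2% v 5.5% | 2.9% v 0.05% |
| 20 ms, Day 1 onward | 55.1% v 5.5% | 31.6% v 0.04% |
| 10 ms, Day 1 and Cycle 2 ECGs only | 15.3% v 2.2% | 1.4% v 0.01% |
| 10 ms, only after Day 1 | 21.6% v 21.3% | 2.5% v 2.4% |

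A shift present on Day 1 that persists is removed almost entirely. A shift that first appears later is not hidden. A shift that recurs after injection cancels at the Cycle 2 ECG, the only later one with fixed post-dose timing.

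**The case against.** The strongest reply is that SAP 4.2 is a loose general sentence, not a chosen ECG baseline. SAP 5.4.3 already places records after the first dose in post baseline, Protocol 12.1.4 requires a pre-dose value, and SAP 1 says the SAP is to be read with the protocol. A careful programmer might therefore use screening. That is a fair reading of the intent. But SAP 5.4.3 never says what the ECG baseline is, and Protocol 12.1 states "The SAP may modify the plans outlined in the protocol", so the protocol does not override SAP 4.2. A program that follows SAP 4.2 by date will pick Day 1. It is also fair that double counting is not certain: if SAP 5.4.3 is programmed by date, Day 1 may drop out of post baseline.

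The second reply concerns size, and most of it stands. Every shift and SD above is assumed. In monkeys both peptides were below quantification from 0.5 hours after dosing (Protocol 4.3.3.2.1), and the monkey toxicity study found no ECG effect (4.3.3.1.3). The enrichment schedule gives no PD-1 inhibitor on Day 1. With no shift, the rules differ by 6.5% − 5.4% = 1.1 percentage points, about 0.1 patient in 10. The tables are descriptive, no decision rule uses QTcF, and the ECG listing lets a reader recompute. These points limit the consequence; they do not make a post-dose reference correct.

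**Conclusion.** The SAP is wrong as written for Phase 1b ECGs. The rule selects a post-dose record as baseline, conflicts with Protocol 12.1.4, and is not cured elsewhere in the SAP. Confidence is high on the text and on the schedule; no effect on actual results is claimed.

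- **Reach:** shown for the enrichment cohort, 10 planned. The assessment schedules in force for the 13 dose-search patients (Protocol 4.3.2) and for any Phase 2 patients enrolled under Amendment 4 are not in the documents. Phase 2 patients on the current Table 9 are unaffected.
- **Size:** it depends wholly on whether QTcF has moved by the Day 1 ECG. In 10 patients with an assumed persistent 10 ms shift, the expected number with a maximum change above 30 ms is about 2.4 from screening against 0.6 under SAP 4.2 at SD 10, and 0.29 against 0.005 at SD 5.77.
- **Importance:** it should be corrected before the ECG tables are programmed. It affects descriptive safety summaries, not a decision rule.

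**What to change.** In SAP 4.2, replace the date rule with, for example:

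> Baseline is the last non-missing value before the first dose of any study drug and within 28 days of that dose. A Day 1 assessment that the protocol schedules before injection is taken as pre-dose if its time is not recorded.

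In SAP 5.4.3, add:

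> A Day 1 ECG obtained after DSP-7888 is post baseline only; the last pre-dose (screening) ECG is the baseline. If the ECG time is missing, a scheduled Phase 1b Day 1 ECG under Tables 7 and 8 is treated as post-dose.

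For dose-search patients and any Phase 2 patients treated under Amendment 4, compare the recorded ECG and dose times, or consult the schedule then in force, before assigning baseline.

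The cost is one reworded definition, a short ECG note and a programming change. A screening ECG is already scheduled in both Phase 1b arms, so no new data are needed. Whether ECG clock times were collected depends on the CRF, which is not in the documents; the missing-time rules cover either case for patients on the current schedules.
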